# **Glossary of Abbreviations**

Ab	Antibody
AE	Adverse Event
AIRglu	Acute Insulin Response to Glucose
ALT (SGPT)	Alanine Aminotransferase (serum glutamatepyruvate transaminase)
APC-R	Activated Protein C Resistance
APTT	Activated Partial Thromboplastin Time
AST (SGOT)	Aspartate Aminotransferase (serum glutamicoxaloacetic transaminase)
ATG	Rabbit Anti-Thymocyte Globulin
BG	Blood Glucose
BID	Twice Daily
BMI	Body Mass Index
Boost ®	Liquid Meal Replacement Drink
BW	Body Weight
C3a	Complement Activation Fragment
CBC	Complete Blood Count
CFR	Code of Federal Regulations
CGMS	Continuous Glucose Monitoring System ®
COIMS	Council for International Organization of Medical Sciences
CIT	Clinical Islet Transplantation Consortium
CITR	Collaborative Islet Transplant Registry
CIT-TCAE	CIT Terminology Criteria for Adverse Events
CMV	Cytomegalovirus
CNI	Calcineurin Inhibitor
CPGCR	C-Peptide to Glucose, Creatinine Ratio
CRF	Case Report Form
CTL	Cytotoxic T Lymphocyte
CXR	Chest x-ray
DAIT	Division of Allergy, Immunology, and Transplantation
DCC	Data Coordinating Center
DCCT	Diabetes Control and Complications Trial
DIC	Disseminated Intravascular Coagulation
DMSO	Dimethylsulfoxide
DSMB	Data Safety Monitoring Board

EBV	Epstein-Barr Virus
EC	Ethics Committee
ECG or EKG	Electrocardiogram
EDTA	Ethylenediaminetetraacetric Acid
EMEA	European Medicines Agency
EU-GMP	European Union Good Manufacturing Practices
FDA	Food and Drug Administration
FSIGT	Insulin Modified Frequently Sampled Intravenous Glucose Tolerance Test
GCP	Good Clinical Practice
G-CSF	Granulocyte Colony Stimulating Factor
GFR	Glomerular Filtration Rate
GMP	Good Manufacturing Practice
Hb	Hemoglobin
HbA 1C	Glycosylated Hemoglobin
HBsAg	Hepatitis B Surface Antigen
HCV Ab or anti-HCV	Hepatitis C Antibody
HDL	High Density Lipoprotein
HIV	Human Immunodeficiency Virus
HLA	Human Leukocyte Antigen
HR	Heart Rate
НҮРО	Ryan Hypoglycemia Severity Score
IBMIR	Instant Blood Mediated Inflammatory Reaction
ICH	International Conference on Harmonization
IEQ	Islet Equivalent
Ig	Immunoglobulin
IL-2	Interleukin 2
INR	International Normalized Ratio
IRB	Institutional Review Board (also Ethics Committee)
IRI	Immunoreactive Insulin
ITN	Immune Tolerance Network
ITT	Intent-to-Treat
IU	International Units
IV	Intravenous

JDFI	Juvenile Diabetes Foundation International
kPa	Kilo-Pascal (pressure)
LDL	Low Density Lipoprotein
LFTs	Liver Function Tests
LI	Lability Index
LMW-DS	Low Molecular Weight Sulfated Dextran
MAGE	Mean Amplitude Glycemic Excursion
МНС	Major Histocompatibility Complex
MMF	Mycophenolate Mofetil
MMTT	Mixed-Meal Meal Tolerance Test
MPA-AUC	Mycophenolic Acid- Area Under the Curve
NCI-CTCAE	National Cancer Institute- Common Toxicity Criteria for Reporting Adverse Events
NIAID	National Institute of Allergy and Infectious Diseases (United States)
NIDDK	National Institute of Diabetes & Digestive & Kidney Diseases (United States)
NIH	National Institutes of Health (United States)
РВМС	Peripheral Blood Mononuclear Cells
PCR	Polymerase Chain Reaction
PET	Positron Emissions Tomography
PI	Principal Investigator
pit-hGH	Pituitary Growth Hormone
PML	Progressive Multifocal Leukoencephalopathy
PNF	Primary Non-Function
РО	Orally
PRA	Panel Reactive Antibodies
РТ	Prothrombin Time
РТТ	Partial Thromboplastin Time
PT-INR	Prothrombin- International Normalized Ratio
PTLD	Post Transplant Lymphoproliferative Disease
QD	Every Day
QOL	Quality of Life
RNA	Ribonucleic Acid
SAE	Serious Adverse Event
SAEC	Safety Adverse Event Coordinator

SAP	Statistical Analysis Plan
SC	Subcutaneous
SGOT (AST)	Serum Glutamic-oxaloacetic Transaminase
SGPT (ALT)	Serum Glutamate Pyruvate Transaminase
SMT	Standard Medical Treatment
SOP	Standard Operating Procedure
SPC	Summary of Product Characteristics
SSL	Secure Sockets Layer
SUSARs	Suspected Unexpected Serious Adverse Reactions
T1D	Type 1 Diabetes
ТАТ	Thrombin-Antithrombin
ТВ	Tuberculosis
TCAE	Terminology Criteria for Adverse Events
TF	Tissue Factor
ULN	Upper Limit of Normal
UNOS	United Network for Organ Sharing
WHO	World Health Organization

# **Study Definitions Page**

Control Arm- State of the Art	The study treatment group randomized to receive protocol specified immunosuppression without LMW-DS, including anticoagulative treatment with Heparin with the islet infusion.
Experimental Arm- Low Molecular Weight Sulfated Dextran	The study treatment group randomized to receive protocol specified immunosuppression with Low Molecular Weight Sulfated Dextran (LMW-DS), and excluding Heparin treatment.
Full Islet Graft Function	
 
Islet transplant recipients are considered to have full islet graft function if all of the following criteria are met: 
 
Titrated off insulin therapy for at least 1 week (7 consecutive days) with the last day within the day 75 and day 365 windows;
 
One HbA1c level, one fasting serum glucose level, and Mixed Meal Tolerance Test are documented within the visit window (e.g. 70-80 days at Day 75) and 7 consecutive days of blood sugar and insulin readings are documented within +/- 7 days of the visit window (e.g. 63-87 days at Day 75);
 
HbA1c <7.0% or a ≥2.5% decreased from baseline;
 
Fasting capillary glucose level should not exceed 140 mg/dL (7.8 mmol/L) more than three times in the 7 consecutive days (fasting is defined as 1st blood sugar reading of the day not noted as post-prandial or bedtime). Post-prandial capillary glucose level ≤ 126 mg/dL (≤7.0 mmol/L) at 90 minutes during the MMTT;
 
Fasting serum glucose level ≤ 126 mg/dL (≤7.0 mmol/L) from central lab results; if the fasting serum glucose level is > 126 mg/dL (>7.0 mmol/L), it must be confirmed in an additional one out of two measurements;
 
At least one MMTT fasting or stimulated c-peptide ≥0.5 ng/ml.
 
 
 

Graft Failure	Islet allograft failure will be defined as absence of insulin production by transplanted islets, as evidenced by absence of c-peptide <0.1nmol/L (<0.3 ng/mL). This will be determined by: (1) c-peptide <0.1nmol/L (<0.3 ng/mL) on random testing, followed by (2) c-peptide <0.1nmol/L (<0.3 ng/mL) at baseline, and at 60 and 90 minutes after MMTT. C-peptide levels obtained in the course of the MMTT levels will be run at the core laboratory in Seattle, WA. Subjects with graft failure do not need to complete the day 75 metabolic assessment.
Immune Sensitization Insulin Dependent	Defined by detecting anti-HLA antibodies not present prior to transplantation Islet transplant recipients who do not meet the criteria for full islet graft function will be
Intensive Diabetes Management	considered insulin-dependent. Self monitoring of glucose values no less than a mean of three times each day averaged over each week and by the administration of three or more insulin injections each day or insulin pump therapy.
Partial Graft Function	Islet transplant recipients who do not meet criteria for full islet graft function but have either a basal or stimulated C-peptide level $\geq 0.1$ nmol/L ( $\geq 0.3$ ng/L).
Primary Non- Function	Graft failure that occurs between 3-7 days post-transplant. Participants with graft failure do not need to complete the day 75 metabolic assessments.
Progressive Renal Dysfunction	A creatinine rising above 2.0 mg/dL (177 $\mu$ mol/L) with calcineurin inhibitor trough levels within maintenance levels.

Protocol Eligible	After completion of the screening assessments required to confirm eligibility, the subject is considered "protocol eligible".
Severe Hypoglycemic Event	A severe hypoglycemic event is defined as an event with one of the following symptoms: memory loss; confusion; uncontrollable behavior; irrational behavior; unusual difficulty in awakening; suspected seizure; seizure; loss of consciousness; or visual symptoms, in which the subject was unable to treat him/herself and which was associated with either a blood glucose level < 54 mg/dL (3.0 mmol/L) or prompt recovery after oral carbohydrate, IV glucose, or glucagon administration.
Wait List	Protocol eligible subjects who have been listed for islet transplant on the Nordic islet transplant wait list.

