#### Full Islet Graft Function Definition

Safety

Secondary

Endpoints

- Islet transplant recipients are considered to have full islet graft function if all of the following criteria are met:
- Titrate off insulin therapy for at least 1 week (7 consecutive days) with the last day within the day 75 and 365 day windows;
  - One HbA1c level, one fasting serum glucose level, and Mixed Meal Tolerance Test are documented within the visit window (e.g. 70-80 days at Day 75) and 7 consecutive days of blood sugar and insulin readings are documented within +/- 7 days of the visit window (e.g. 63-87 days at Day 75);
  - HbA1c < 7.0% or a ≥2.5% decrease from baseline;

  - Fasting capillary glucose level should not exceed 140 mg/dL (7.8 mmol/L) more than three times in the 7 consecutive days (fasting is defined as 1st blood sugar reading of the day not noted as post-prandial or bedtime).
  - Post-prandial capillary glucose should not exceed 180 mg/dL (10.0 mmol/L) at 90 minutes during the MMTT;
  - Fasting serum glucose level ≤ 126 mg/dL (≤7.0 mmol/L) from central lab results; if the fasting serum glucose level is > 126 mg/dL (>7.0 mmol/L), it must be confirmed in an additional one out of two measurements;
  - At least one MMTT fasting or stimulated c-peptide ≥ 0.5 ng/ml.

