### 4.1.3 Efficacy Endpoints

### At 75 ± 5 days following the first infusion:

- The percent reduction in insulin requirements
- HbA1c
- Mean amplitude of glycemic excursions (MAGE)
- Glycemic lability index (LI)
- Clarke hypoglycemia awareness score
- Ryan hypoglycemia severity (HYPO) score
- Basal (fasting) glucose and c-peptide and 90-min glucose derived from the mixed-meal tolerance test
- β-score
- C-peptide:glucose creatinine ratio
- Acute insulin response to glucose (AIRglu), insulin sensitivity, and disposition index derived from the insulin-modified frequently-sampled intravenous glucose tolerance (FSIGT) test
- Glucose variability and hypoglycemia duration derived from the continuous glucose monitoring system® (CGMS)
- The proportion of subjects with full islet graft function.

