### 4.1.3.1 FULL ISLET GRAFT FUNCTION DEFINITION:

Islet transplant recipients are considered to have full islet graft function if all of the following criteria are met:

- Titrated off insulin therapy for at least 1 week (7 consecutive days) with the last day within the day 75 and day 365 windows;
- HbA1c <7.0% or a 2.5%% decreased from baseline at the end of the 7 day period when titrated off insulin;
- Fasting capillary glucose level should not exceed 140 mg/dL (7.8 mmol/L) more than three times in the past week (based on measuring capillary glucose levels a minimum of 7 times in a seven day period);
- 2-hour post-prandial capillary glucose should not exceed 180 mg/dl (10.0 mmol/L) more than three times in the past week (based on measuring capillary glucose levels a minimum of 21 times in a seven day period);
- Fasting serum glucose level ≤ 126 mg/dL (≤7.0 mmol/L) from central lab results; if the fasting serum glucose level is > 126 mg/dL (>7.0 mmol/L), it must be confirmed in an additional one out of two measurements;
- Evidence of endogenous insulin production defined as fasting or stimulated C-peptide levels ≥ 0.5 ng/mL (≥0.16 nmol/L) at the end of the 7 day period when titrated off insulin.

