### 9.1.1 Study Endpoints

Designated primary and secondary endpoints will be employed to compare each treatment group ("LMW-DS" and "State of the Art"). Because the assessment of islet graft function is dependent on complex physiologic relationships between the graft and its recipient, a number of different tests will be performed. The stimulated c-peptide for the Mixed Meal Tolerance Test (MMTT) will be used as the primary endpoint, and additional stimulatory tests of islet graft function utilizing glucose (FSIGT) challenges will be performed to assess secondary endpoints. Also, the effect of islet graft function on glycemic control (HbA1c), glycemic lability (MAGE and LI), hypoglycemia (Clarke and HYPO scores), glucose variability (CGMS), and quality of life (QOL) will be assessed as additional secondary endpoints. (See section 4.1 for endpoint description).

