#### 9.1.1.5 MIXED-MEAL TOLERANCE TEST (MMTT)

Basal (fasting) and stimulated glucose and c-peptide levels will be determined using the MMTT. Subjects will be instructed not to eat or inject short-acting (or bolus) insulin after 8 PM the night before the test. Evening or bedtime administration of long-acting insulin will be permitted, as will consumption of water. Subjects receiving CSII (insulin "pump" therapy) may remain on the basal rate of insulin. Subjects will arrive fasting to the transplant or diabetes clinic where the capillary BG will be checked. If the BG is < 70 mg/dL (3.9 mmol/L) or > 136 mg/dL (8.0 mmol/L), the test will be rescheduled for the next possible day. If the BG is 70 – 136 mg/dl (3.9-8.0 mmol/L), basal glucose and c-peptide levels will be drawn. Immediately after, the subject will receive 6 ml per kg body weight (to a maximum of 360 mL) of Boost® High Protein Drink or Resource Protein Drink (or a nutritionally equivalent substitute) to consume in 5 minutes starting at time = 0. Then, at time =15, 30, 60, 90 and 120 minutes, stimulated glucose and c-peptide levels will again be drawn.

Each blood sample for c-peptide and glucose determination will be drawn according to University of Washington (Seattle, WA) standard protocol. Each sample will be shipped frozen to the University of Washington for measurement by the core laboratory.

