#### **10.2.2 SECONDARY ENDPOINTS**

The secondary endpoints are defined in section 3.1.2.

HbA1c levels will be categorized for example, as either normal (<= 7.0 %), or non-normal (>7.0%). Dichotomous variables such as HbA1c (normal/non-normal) and rate of severe hypoglycemic events will be analyzed using logistic regression analysis with a term for treatment. Should a dichotomous endpoint not be evaluated for a particular individual then a failure will be imputed unless an evaluation is done at a time longer than 75 days after transplant and before an additional islet cell infusion, in which case that later value will be imputed.

Continuous variables such as QOL scales will be analyzed by a t-test. If there is compelling evidence that the normal distribution does not hold then a logarithmic or square root transformation will be done before using the t-test. If lack of normality persists, non-parametric tests will be used.

By examining multiple secondary endpoints it is likely that some variables will be found significantly different between the two treatment groups, but these findings may be Type I errors. Appropriate qualifiers will be reported with any significant secondary findings.

Regression models for longitudinal data (mixed models) will be used to examine the differences between groups in each of the response variables (HbA1c level and C-peptide levels) where measurements are repeated over time. Mixed models for dichotomous variables will be used to model full islet graft function over time. Survival analysis models will be used to compare time to becoming insulin dependent and to identify risk factors through Kaplan-Meier estimates and Cox regression models.

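### Full islet graft function, a secondary efficacy endpoint, has three conflicting post-prandial glucose criteria in current protocol text, and nothing says which one governs

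*Protocol*

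**What the plan says.** Section 4.1.3 lists as an efficacy endpoint "The proportion of subjects with full islet graft function", at Day 75 after the first infusion and again at Day 365 after the first and final infusion. The Synopsis labels these secondary efficacy endpoints. Section 10.2.2 adds an analysis over time: "Mixed models for dichotomous variables will be used to model full islet graft function over time".

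Three current passages define the term, each as a list in which all items must be met. Their post-prandial items are:

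- Study Definitions Page: "Post-prandial capillary glucose level ≤ 126 mg/dL (≤7.0 mmol/L) at 90 minutes during the MMTT".
- Synopsis, Full Islet Graft Function Definition: "Post-prandial capillary glucose should not exceed 180 mg/dL (10.0 mmol/L) at 90 minutes during the MMTT".
- Section 4.1.3.1: "2-hour post-prandial capillary glucose should not exceed 180 mg/dl (10.0 mmol/L) more than three times in the past week", resting on at least 21 capillary measurements in seven days. This list contains no MMTT glucose limit.

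Section 9.1.1 tells the reader "See section 4.1 for endpoint description". No section states that one definition overrides the others.

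**The concern.** Because every criterion must be met, the post-prandial item alone can decide whether a subject is a responder. If the three texts set different rules for that item, the same subject with the same data can be counted in or out depending on which page is followed.

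The Day 75 proportion, the Day 365 proportions and the mixed model in 10.2.2 would all inherit that choice. The trial is open label (7.8.1), so a definition left unsettled could end up being chosen when results by arm are already visible. Section 7.4.2 also relies on the term when further infusions are considered, so sites as well as analysts work from it.

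**Working it through.** **1. Is it a unit slip?** Convert each cut-off with mg/dL ÷ 18.016:

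- 126 ÷ 18.016 = 6.99 mmol/L (stated 7.0)
- 180 ÷ 18.016 = 9.99 mmol/L (stated 10.0)

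Each text agrees with itself. The gap is real: 180 − 126 = 54 mg/dL, or 10.0 − 7.0 = 3.0 mmol/L.

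**2. Classify example 90-minute MMTT values, all other criteria met.**

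| 90-min glucose (mg/dL) | Definitions Page (≤126) | Synopsis (≤180) |
|---|---|---|
| 120 | pass | pass |
| 126 | pass | pass |
| 127 | fail | pass |
| 150 | fail | pass |
| 180 | fail | pass |
| 181 | fail | fail |

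The first rule is nested within the second. They disagree for values above 126 and up to 180 mg/dL.

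**3. Add 4.1.3.1.** It uses a different measurement, so it can differ from both. A subject at 181 mg/dL fails both MMTT rules but passes 4.1.3.1 if no more than three 2-hour readings in the week exceed 180. A subject at 120 mg/dL passes both MMTT rules but fails 4.1.3.1 with four such readings.

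**4. Size per subject.** With 18 subjects per arm (section 7.3) as the denominator:

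- one reclassified subject in an arm: 1/18 = 5.6 percentage points
- two: 2/18 = 11.1
- three: 3/18 = 16.7

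The protocol gives no distribution of 90-minute glucose, so the number of such subjects cannot be derived.

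**5. Can the 4.1.3.1 rule be met from the diary?** Section 7.6 asks for a reading at each of three meals, one two hours after each, and one in the evening: 3 + 3 + 1 = 7 a day, of which 3 are post-prandial. Over 7 days that is 3 × 7 = 21 post-prandial values, which matches the 21 in 4.1.3.1. Once a subject is insulin-free, sections 7.6 and 9.1 accept two days a week: 3 × 2 = 6 post-prandial values, or 7 × 2 = 14 readings of any kind. Both fall short of 21, and full function itself requires being off insulin.

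**6. Where the endpoint sits.** Section 4.1.3 lists 12 items at Day 75 and 15 at Day 365. Full graft function is one item in each list.

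**The case against.** The strongest reply is that the text already points to an answer. Section 4.1.3.1 is the body definition under the endpoint heading, and 9.1.1 sends the reader to section 4.1. This lowers the ambiguity but does not remove it. A pointer is not a precedence rule, and the Definitions Page and Synopsis share an MMTT-based structure that 4.1.3.1 lacks. The SAP is not among the documents at hand and may name one version, but the protocol that sites use would still carry three.

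A second reply is that impact is limited: this is one of many secondary items, and 10.2.2 already promises qualifiers on significant secondary findings. That stands and bounds the severity.

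Several stronger readings are tempting and are not supported:

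- *The 126 and 180 limits cannot both hold.* They can, since any value up to 126 satisfies both. The conflict is in classification.
- *The 126 limit is shown to be an error by nearby text.* The same bullet says "Fasting capillary glucose level should not exceed 140 mg/dL (7.8 mmol/L) more than three times in the 7 consecutive days", which is 140 − 126 = 14 mg/dL above the post-meal limit. Section 9.1.1.5 says "If the BG is 70 – 136 mg/dl (3.9-8.0 mmol/L), basal glucose and c-peptide levels will be drawn", so a test may start 136 − 126 = 10 mg/dL above it. Both are weak support. The fasting figure concerns home readings with three exceedances tolerated, and the starting rule applies to all subjects, including those on insulin. The Definitions Page also sets fasting serum glucose at 126 mg/dL, equal to the 90-minute limit. A copying slip from that item is plausible, but the document does not say so. Section 9.1.1.6 links 180 mg/dL at 90 minutes with a β-score of 8 and sets no threshold for this endpoint.
- *The lability index already supplies the readings.* Section 9.1.1.3 needs four or more a day, so 4 × 7 = 28 a week, but at unspecified times. That does not show that 21 post-prandial values exist.
- *The conflict changes the number of infusions or the time to insulin dependence.* Absence of full function is only one of ten conditions for a third infusion in 7.4.2. The protocol does not show how either outcome would shift, so no such effect is claimed.

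**Conclusion.** The inconsistency is real and should be fixed. Three current definitions of one secondary endpoint give different post-prandial rules, and applying them to the same data can give different responder proportions at Day 75 and Day 365 and different inputs to the model in 10.2.2.

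The size is 5.6 percentage points in an arm per affected subject, assuming a denominator of 18 and that the subject meets every other criterion. How many subjects this involves is unknown and may be none. The primary endpoint (90-minute C-peptide at Day 75), the sample size and the stopping boundaries do not use this definition and are untouched.

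**What to change.** Before any subject is classified:

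1. Keep one definition, in 4.1.3.1, and replace the lists on the Definitions Page and in the Synopsis with a cross-reference. Add the same cross-reference in 7.4.2.
2. Delete the 126 mg/dL post-prandial limit.
3. Choose one of two versions:
   - **MMTT version (90-minute value not above 180 mg/dL).** Name the specimen as the core-laboratory 90-minute MMTT glucose. The Definitions Page and Synopsis both call it capillary, whereas 9.1.1.5 specifies a capillary check only on arrival and sends the timed samples to the core laboratory. With that wording no new test is needed: Appendix 1 already schedules the MMTT at Day 75, Month 12 and one year after the first transplant.
   - **Weekly version as in 4.1.3.1.** State in 7.6 and 9.1 that the two-days-a-week minimum does not apply in the assessment week. Insulin-free subjects must then record on all 7 days, including three 2-hour post-prandial values a day.

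Either choice is defensible; the sponsor should make it once.

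The cost is a wording amendment. Section 13.1 requires ethics approval and submission to the health authorities before it takes effect. If the sponsor regards the endpoint definition as a principal feature, the DSMB and sponsor review in 10.7 also applies.

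### Insulin dependence is defined as failing any part of a graft-function composite, so the planned time-to-insulin-dependence analysis would not describe return to insulin

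*Protocol*

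**What the plan says.** The Study Definitions Page gives the term no insulin-use condition of its own: "Islet transplant recipients who do not meet the criteria for full islet graft function will be" "considered insulin-dependent".

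Full function is a conjunction: "Islet transplant recipients are considered to have full islet graft function if all of the following criteria are met". Insulin use enters through one item: "Titrated off insulin therapy for at least 1 week (7 consecutive days) with the last day within the day 75 and day 365 windows". The other items are laboratory, home-glucose and documentation conditions. Among them are "One HbA1c level, one fasting serum glucose level, and Mixed Meal Tolerance Test are documented within the visit window", the HbA1c limit ("HbA1c < 7.0% or a ≥2.5% decrease from baseline" in the Synopsis) and, on the Study Definitions Page, "Post-prandial capillary glucose level ≤ 126 mg/dL (≤7.0 mmol/L) at 90 minutes during the MMTT".

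Section 10.2.2 then puts the term to use: "Survival analysis models will be used to compare time to becoming insulin dependent", with Kaplan-Meier estimates and Cox models. No other definition of that event appears in the protocol.

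**The concern.** The complement of an all-criteria composite is failure of any one criterion. A recipient who has stopped insulin and stays off it can therefore be recorded as insulin-dependent because of an HbA1c result, a meal-test glucose or a gap in the records. A reader of a curve labelled time to insulin dependence will take it to show when recipients went back on insulin. The protocol uses the words that way itself: sections 1.1.1 and 9.2 treat insulin independence as being off, or free of, insulin. With 18 subjects per arm, a few relabelled subjects can visibly move a Kaplan-Meier curve or a Cox estimate.

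**Working it through.** The plan states no figure on this point, so the check is of logic, followed by an illustration of size.

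**1. The three versions of full islet graft function**

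| Criterion | Study Definitions Page | Synopsis | Section 4.1.3.1 |
|---|---|---|---|
| Off insulin 7 days | yes | yes | yes |
| HbA1c, fasting glucose and MMTT documented in window | yes | yes | not listed |
| Home readings | 7 consecutive days | 7 consecutive days | at least 7 fasting and 21 post-prandial in 7 days |
| HbA1c <7.0% or fall of at least 2.5% | yes | yes | yes |
| Fasting capillary >140 mg/dL | fails if more than three times | same | same |
| Post-prandial glucose | one 90-minute MMTT value, limit 126 mg/dL | one 90-minute MMTT value, limit 180 mg/dL | fails if more than three 2-hour values exceed 180 mg/dL |
| Fasting serum >126 mg/dL | fails if confirmed | same | same |
| C-peptide ≥0.5 ng/mL | yes | yes | yes |

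The insulin-dependence event inherits whichever version is applied.

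**2. Records of recipients taking no insulin, read literally**

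- *HbA1c 7.1%.* Reading the 2.5% fall as percentage points, the alternative limb is met only if baseline was at least 7.1 + 2.5 = 9.6%. Eligibility admits HbA1c up to 10%, so this rescues baselines of 9.6% to 10%. With a lower baseline the recipient is insulin-dependent under all three versions, on one unconfirmed value.
- *90-minute MMTT glucose 150 mg/dL.* Insulin-dependent under the Study Definitions Page, not under the Synopsis; section 4.1.3.1 has no such criterion. Section 9.1.1.6 associates values up to 180 mg/dL, with the top β-score, with excellent function.
- *Fasting serum glucose 7.2 mmol/L, confirmed.* Insulin-dependent under all three versions.
- *MMTT not documented in the window.* Fails the Study Definitions Page and the Synopsis. Under section 10.2.2 a later value obtained before another infusion can stand in for an unevaluated dichotomous endpoint; otherwise failure is imputed.

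**3. The recording rule.** Sections 7.6 and 9.1 allow a subject who is free of insulin to record glucose on two days per week. At one fasting and three post-meal readings per day, that gives 2 × 1 = 2 fasting and 2 × 3 = 6 post-meal readings. The composite needs 7 consecutive days of readings, or in section 4.1.3.1 at least 7 and 21. A subject using this allowance can fail the composite because insulin was stopped.

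**4. Dating.** The insulin-free criterion is tied to the day-75 and day-365 windows. The nominal gap is 365 − 75 = 290 days. Insulin dose, by contrast, is recorded daily (section 9.1.1.1).

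**5. Illustration of size.** The documents give no failure rates for insulin-free recipients. Assume a rate q for each of three routes (HbA1c, 90-minute glucose, missing test), taken as independent. The share labelled dependent while taking no insulin is 1 − (1 − q)³:

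- q = 5%: 1 − 0.95³ = 14.3%, or 2.6 of 18
- q = 10%: 1 − 0.90³ = 27.1%, or 4.9 of 18
- q = 20%: 1 − 0.80³ = 48.8%, or 8.8 of 18

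The counts suppose that a whole arm of 18 is insulin-free. Under section 4.1.3.1, HbA1c is the main single-value route. On that route alone the share is q itself: 0.9, 1.8 or 3.6 of 18. Under a definition by insulin use alone it is zero by construction.

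**The case against.** The best case for the plan has five parts.

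- *The composite is defensible.* The trial is open-label, so restarting insulin is decided knowing the arm. A composite that includes central-laboratory HbA1c and glucose is less open to that influence. This stands as a reason to keep the composite, but not to call it insulin dependence.
- *The routes are narrower than they look.* A reader might infer that any one abnormal glucose or any missed test is enough. The documents do not support that. Fasting serum glucose needs confirmation, three fasting capillary exceedances are tolerated, and a later value can replace a missed test. Only the 90-minute MMTT value works as a single glucose, and only in two of the three versions. The two-day recording rule is a minimum, and the lability index at the same visits calls for four or more readings daily over four weeks (section 9.1.1.3), so many subjects may have more.
- *A state is not an event.* A recipient who first fails at day 75 was never classed as having full function. Whether that counts as becoming dependent turns on the risk set, which section 10.2.2 does not state. This stands: the percentages above are shares carrying the label, not event rates.
- *Dating may be finer.* HbA1c, MMTT and blood-sugar records are also scheduled at month 6, and visits restart after a repeat transplant. So 290 days is a worst case.
- *The SAP may settle it.* Section 10.2 leaves details there. But the Study Definitions Page already fixes the term: an SAP that follows it repeats the problem, and one that departs from it contradicts the protocol.

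**Conclusion.** The point holds. Read as written, the protocol labels some recipients who take no insulin as insulin-dependent and uses that label as the event in a survival analysis. The result would describe loss of a graft-function composite, dated by visit, and not return to insulin.

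The logic needs no assumed rate. The size does: the 14% to 49% range rests on assumed failure rates and on independence, and overlap between criteria would lower it. No single figure can be supported from the documents. The HbA1c route also assumes that the 2.5% fall means percentage points.

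The reach is limited. Time to insulin dependence is not among the endpoints listed in section 4.1, and percent reduction in insulin requirements is reported separately. A reader might infer bias between the arms or an effect on the primary endpoint. Neither is supported: the definition applies to both arms alike, and the primary endpoint is the 90-minute C-peptide level. It is a defect in one secondary analysis, and worth correcting because correction is cheap.

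**What to change.** - On the Study Definitions Page and in section 10.2.2, define the insulin-dependent event by sustained exogenous insulin use taken from the daily insulin diary, dated to the first day of that use. State what counts as sustained.
- Report loss of full islet graft function as a separate, visit-based outcome under that name. Showing both also answers the open-label objection to relying on insulin use alone.
- Reconcile the three versions of full islet graft function (Study Definitions Page, Synopsis, section 4.1.3.1), and reconcile the two-days-per-week recording allowance in sections 7.6 and 9.1 with the readings that the composite requires.

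The cost is mainly wording. Subjects already record total daily insulin dose (section 9.1.1.1), and Appendix 1, note 5, requires the diary log at each visit. One practical check is needed: note 15 describes the insulin-requirement item as the dose on the day before the visit, so the date of restarting may have to be taken from the diary and entered as one extra item. No new test or visit is required.
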